**Research on the Construction of a Prognostic Model for COPD
Complicated with Sarcopenic Obesity Based on Bioelectrical
Impedance Phase Angle Technology (COSAT)**

Research Protocol

Main researchers: [name], [name]

Clinical research department: Respiratory and Critical Care

Medicine Sponsor: [name]

Ethics Review No.:2025K200

Scheme Version No: 01

Plan Preparation date: July 15th, 2025

Research Objectives:

This study aims to explore the diagnosis, impact, and prognostic factors of COPD complicated with sarcopenic obesity using multi-segment bioelectrical impedance phase angle technology. It seeks to clarify the diagnostic value and efficacy of body composition analysis in specific populations, analyze the relationship between phase angle and COPD severity as well as quality of life, investigate its predictive role for adverse outcomes, and reveal the effects of inflammation and metabolic disorders in sarcopenic obesity. The goal is to provide a basis for early screening and precise intervention to improve patient prognosis.

Proposed Research Methods

Inclusion Criteria

- (1) Age over 65 years;**
- (2) Ability to complete physical activity assessments and pulmonary function tests;**
- (3) Complete medical records, willingness to adhere to follow-up arrangements, and provision of adverse event reports via telephone or outpatient visits, with signed informed consent;**
- (4) COPD diagnosis based on the American Thoracic Society (ATS)/European Respiratory Society (ERS) GOLD definition, with a post-bronchodilator FEV1/FVC ratio < 0.70, current or former smokers with a smoking history of ≥ 10 pack-years.**

Exclusion Criteria:

- (1) Severe cognitive impairment or hand deformities (e.g., rheumatoid arthritis) preventing body composition measurements;**
- (2) Incomplete clinical or follow-up data or unwillingness/inability to undergo regular follow-up;**
- (3) Severe systemic edema;**
- (4) Presence of cardiac pacemakers or significant metal implants that may interfere with measurements;**
- (5) Voluntary withdrawal for any reason, including loss to follow-up.**

Data Collection:

Demographic and clinical data: Gender, smoking status (never, former, current), age, height, weight, waist circumference, BMI, skeletal muscle index (SMI), body fat content,

visceral fat index, and segmental phase angles measured via bioelectrical impedance analysis.

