Clinical records: Smoking history, comorbidities (Charlson Comorbidity Index), nutritional status (MNA-SF), physical performance (SPPB), medication use, pulmonary function tests, COPD exacerbations in the past year, CAT score, mMRC score, and St. George's Respiratory Questionnaire (SGRQ).

Laboratory tests: Blood samples for CBC, CRP, cholesterol, albumin, HbA1c, IL-6, and TNF- α (ELISA).

Sample Size Calculation:

Using PASS 15.0 for repeated-measures ANOVA ($\alpha = 0.05$, power = 90%), with a COPD prevalence of 15% and a 2:1 ratio for sarcopenic obesity vs. non-sarcopenic groups, the study requires 200 participants (33 sarcopenic obese, 33 non-obese sarcopenic, 72 obese non-sarcopenic, and 72 non-obese non-sarcopenic).

Diagnostic Criteria:

Sarcopenia: Asian Working Group criteria: SMI (InBody S10) $<7.0 \text{ kg/m}^2$ (men) or $<5.7 \text{ kg/m}^2$ (women); grip strength $<28 \text{ kg}$ (men) or $<18 \text{ kg}$ (women); gait speed $<0.8 \text{ m/s}$. **Obesity:** BMI $\geq 28 \text{ kg/m}^2$ or waist circumference $\geq 85 \text{ cm}$ (men)/ $\geq 80 \text{ cm}$ (women); body fat $\geq 24.3\%$ (men) or $\geq 33.2\%$ (women).

sarcopenic Obesity: Coexistence of sarcopenia and obesity.

Assessments:

Physical Performance: Short Physical Performance Battery (SPPB: balance, gait speed, chair stands; score 0–12).

Nutritional Status: Mini Nutritional Assessment (MNA-SF; score 0–12).

Phase Angle: Measured via InBody S10 at six frequencies (1kHz–1000kHz) across five body segments, calculated using resistance (R) and reactance (Xc):

$\text{PHA} = \arctan((\text{Xc_right arm} + \text{Xc_trunk} + \text{Xc_right leg}) / (\text{R_right arm} + \text{R_trunk} + \text{R_right leg})) \times 180^\circ / \pi$.

Follow-up Endpoints:

Primary: Changes in pulmonary function, dyspnea scores, and body composition at 2 years.

Secondary: Acute exacerbations, hospitalizations, or death within 2 years. Follow-ups at 6, 12, and 24 months.

Grouping patients based on whether they have sarcopenic obesity, the differences in clinical data between the two groups were analyzed. Statistical analysis was performed using SPSS 24.0 statistical software.

Analysis of Demographic Characteristics and Clinical Data:

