The age and gender distribution of the patients were described. Based on whether the patients had sarcopenic obesity, they were divided into two groups. The differences in clinical data between the two groups, including age distribution, smoking status, obesity-related body fat, pulmonary function, whole-body and segmental phase angle, were analyzed. Continuous variables were expressed as mean \pm standard deviation, and categorical variables were expressed as percentages. Differences between groups were analyzed using Student's t-test for continuous variables and the chi-square test for categorical variables, depending on the data type.

Analysis of Factors Associated with COPD Complicated by Sarcopenic Obesity:

Univariate and multivariate analyses were conducted on data from COPD patients with sarcopenic obesity. Using clinical data variables, nutritional status, physical activity capacity, whole-body and segmental phase angle, logistic regression was applied to analyze the factors associated with sarcopenic obesity in COPD patients.

Analysis of the Prognostic Predictive Value of Sarcopenic Obesity in Obstructive Pulmonary Disease:

The differences in hospital stay length, acute exacerbation readmission rate, and mortality between COPD patients with sarcopenic obesity and those without sarcopenia at baseline were compared. Kaplan-Meier analysis was used for statistical analysis, and differences were expressed using the log-rank test.

COSAT study

INFORMED CONSENT FORM

This document provides you with information to help you decide whether to participate in this clinical research study. Please read it carefully. If you have any questions, please direct them to the researcher in charge of this study.

Your participation in this study is voluntary. This research has been reviewed and approved by the institutional ethics review committee of our research institution.

The background, objectives, research process, and other important information are as follows:

Research Purpose:

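### The primary endpoint, change over two years, has no specified analysis, and two exclusion criteria, if applied as written, would confine it to completers

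*Combined protocol and SAP*

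**What the plan says.** Under Follow-up Endpoints, the primary endpoint is "Changes in pulmonary function, dyspnea scores, and body composition at 2 years". The secondary endpoint is "Acute exacerbations, hospitalizations, or death within 2 years", and the schedule is "Follow-ups at 6, 12, and 24 months".

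The Sample Size Calculation begins "Using PASS 15.0 for repeated-measures ANOVA", with alpha 0.05 and 90% power, and arrives at 200 participants, split as "33 sarcopenic obese, 33 non-obese sarcopenic, 72 obese non-sarcopenic, and 72 non-obese non-sarcopenic". It names no outcome, no visits and no tested term.

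The analysis text has three parts:
- The section on demographic characteristics and clinical data splits patients by sarcopenic obesity, yes or no. Pulmonary function, body fat and phase angle are among the variables listed. The method is: "Differences between groups were analyzed using Student's t-test for continuous variables and the chi-square test for categorical variables".
- The section on associated factors fits a logistic regression with sarcopenic obesity as the outcome.
- The section on prognostic value compares hospital stay, readmission and mortality by Kaplan-Meier and log-rank. Its comparator is patients without sarcopenia at baseline.

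Two of the Exclusion Criteria bear on follow-up. Exclusion 2 reads "Incomplete clinical or follow-up data or unwillingness/inability to undergo regular follow-up" and exclusion 5 reads "Voluntary withdrawal for any reason, including loss to follow-up".

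**The concern.** A primary endpoint defined as change needs a named variable, a comparator, a time point and a method. The analysis text supplies none of these for the two-year change, and the one longitudinal method in the protocol is confined to the sizing. Whoever analyses the data would have to choose between ANOVA and a t-test, between CAT and mMRC for dyspnoea (both are collected), and between several comparators, with the results in view. The groups are not randomised, so an unadjusted contrast in change also carries confounding by factors such as age.

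The exclusions add a second problem. Withdrawal, loss to follow-up and incomplete follow-up data can be known only after a patient has been enrolled. Removing patients on those grounds selects the analysed sample by what happened during follow-up. If the chance of being lost differs by group and is related to how the patient is changing, the completers' contrast is biased, and no stated analysis would reveal it.

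**Working it through.** **1. The plan's own figure.** The total of 200 cannot be rebuilt, because effect size, SD, within-patient correlation and tested term are not given. Solving backwards at 90% power with four occasions (m = 4), two or four groups and assumed correlation ρ of 0.3 to 0.8:
- Group term, noncentrality N f² m / (1 + (m − 1)ρ): f = 0.16 to 0.25.
- Group-by-time term, noncentrality N f² m / (1 − ρ): f = 0.06 to 0.13.

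Many input sets fit 200, so the figure is neither confirmed nor refuted. The listed groups sum to 33 + 33 + 72 + 72 = 210, not 200.

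**2. Endpoint against analyses.**
- t-test or chi-square: overlaps two primary domains (pulmonary function; body composition through body fat and phase angle). It names no change, no visit and no dyspnoea score.
- Logistic regression: the outcome is group membership, so it does not address change.
- Kaplan-Meier: the outcomes are of the secondary kind.
- Repeated-measures ANOVA: four groups in the sizing, absent from the analysis text.

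**3. Comparators, by the printed counts.** The sizing lists four groups. The t-test sets 33 against 33 + 72 + 72 = 177. Kaplan-Meier sets 33 against 72 + 72 = 144. These counts inherit the conflict between 210 and 200.

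**4. Exclusions.** Exclusion 5 is wholly post-enrolment. In exclusion 2, unwillingness or inability to be followed can be judged at entry; incomplete follow-up data cannot.

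**5. What completer selection could do.** Let d be the proportion lost in a group and g the mean change in retained minus lost patients. The full mean is (1 − d) × retained + d × lost, so the completers' mean differs from it by d × g. The bias in the group contrast is d₁g₁ − d₀g₀, with 1 for sarcopenic obesity and 0 for the comparator. All loss rates and gaps below are assumed:
- Loss 25% v 10%, gap 0.5 SD in both: 0.25 × 0.5 − 0.10 × 0.5 = 0.075 SD. The 33 patients fall to 33 × 0.75 = 24.75, about 25.
- Loss 20% in both, gaps equal at 0.5 SD: 0.
- Loss 20% in both, gaps 1.0 and 0.5 SD: 0.20 × 1.0 − 0.20 × 0.5 = 0.10 SD.
- Loss 10% v 25%, gap 0.5 SD in both: 0.10 × 0.5 − 0.25 × 0.5 = −0.075 SD.

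**6. Scale and precision.** For 33 v 177, two-sided 0.05 (sidedness is not stated) and 90% power, the detectable difference in change is (1.960 + 1.282) × √(1/33 + 1/177) = 0.615 SD. With 167 in the comparator, to match a total of 200, it is 0.618 SD. A bias of 0.075 to 0.10 SD is thus about 12% to 16% of the detectable difference. Assumed loss of 10%, 20% or 30% in both groups lowers power at 0.615 SD to 86.8%, 82.6% or 77.4%.

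**7. Why classical repeated-measures ANOVA is a poor default.** It needs every visit. If each of three follow-up measurements is missed independently by 5% to 10% (assumed), 0.95³ = 86% to 0.90³ = 73% of patients are complete, and 33 falls to about 28 to 24. This matters only if the variables are measured at 6 and 12 months, which the protocol does not state.

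**The case against.** The strongest reply is that an analysis is there, loosely worded. The two-group comparison is introduced directly after the endpoints, and its variable list, which is not exhaustive, covers pulmonary function and body composition. A reader might infer from this point that no analysis touches the primary variables, or that none was intended. The documents do not support that, and the overlap stands. It does not supply a change score, a visit or a dyspnoea score, and the section heading points to a description of patient characteristics.

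Second, exclusions 2 and 5 are listed as eligibility criteria. No analysis set is defined, and nothing says that collected data will be discarded. This also stands: the completer restriction holds only if the criteria are applied as written. A reader might go further and infer a proven bias in a known direction. With no loss rate in the documents, and scenarios on both sides of zero, that is unsupported. Nor does the point extend to the mortality comparison, since death is not named in these exclusions.

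Third, a mixed model over all visits presumes measurements at 6 and 12 months. The protocol gives follow-up times but does not say what is measured at each, so the remedy must allow for both cases.

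Finally, SMI, BMI, waist and body fat define the groups at baseline, so change in them is open to regression to the mean. For SMI, assuming no true change, a single cut-off and 33 v 177, this is about 0.13 SD at a baseline-to-24-month correlation of 0.90, falling to 0.01 SD at 0.99. A reader might conclude that those endpoints should become descriptive. Effects this dependent on assumptions justify a caution in interpretation, not that step. The caution does not apply directly to phase angle, lung function or dyspnoea.

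**Conclusion.** The concern holds in a bounded form and should be corrected before data are analysed. The two-year primary change has no specified variable, visit, comparator or method; this follows from the text alone and needs no assumption. Exclusion 5 and the follow-up-data part of exclusion 2, if applied as written, would limit the estimate to completers. The resulting bias depends on loss being related to group and outcome. The -0.075 to 0.10 SD range illustrates chosen inputs and does not bound the effect. The protocol's 200 can be neither confirmed nor refuted as the size for this endpoint, and it disagrees with its own group counts.

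**What to change.** 1. **Exclusions.** Apply exclusion 5 and the follow-up part of exclusion 2 at enrolment only, to people unwilling or unable to be followed. Keep enrolled patients who later withdraw, miss visits or are lost in the analysis with the data already collected, as consent allows. Report losses and deaths by group.
2. **Primary analysis.** Replace the undated t-test, for the primary endpoint, with a model for change to 24 months in one named variable per retained domain, against one named comparator. State which variables are measured at 6 and 12 months. If they are, use a linear mixed model with group, time and group-by-time. If only baseline and 24 months are measured, model the 24-month value adjusted for baseline; a patient with no 24-month value then adds little, and the report of losses becomes the main safeguard.
3. **Confounders.** Adjust change for a short list already collected, for example age, sex and smoking. In the mixed model these need time interactions, because a main effect shifts all visits equally and cancels out of change. Three covariates at one term each cost 3 × 3 = 9 interaction terms with categorical time, or 3 with linear time. With 33 patients in the smallest group the list should stay short.
4. **Death.** State that the estimate does not represent values after death, and report deaths before 24 months beside it.
5. **Sample size.** Restate it for the same outcome, groups and visits, and reconcile 210 with 200.

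The cost is plan wording, a new sample size calculation and modest extra analysis. The mixed model assumes that missing values are explained by the observed data. Use of withdrawn patients' data depends on consent terms that are not in the copy reviewed.

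### Four sarcopenia-by-obesity groups are sized but no analysis uses them, so the planned contrasts cannot separate sarcopenic obesity from sarcopenia alone or obesity alone

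*Combined protocol and SAP*

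**What the plan says.** All references are to the combined protocol and SAP.

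- **Research Objectives.** The aims include the diagnosis, impact and prognostic factors of COPD with SO, and to "reveal the effects of inflammation and metabolic disorders in sarcopenic obesity".
- **Diagnostic Criteria.** SO is defined as "Coexistence of sarcopenia and obesity". A patient without SO may therefore have sarcopenia only, obesity only, or neither.
- **Sample Size Calculation.** The calculation is for a repeated-measures ANOVA at 90% power. It gives a total of 200, broken down as "33 sarcopenic obese, 33 non-obese sarcopenic, 72 obese non-sarcopenic, and 72 non-obese non-sarcopenic".
- **Paragraph after Follow-up Endpoints.** "Grouping patients based on whether they have sarcopenic obesity, the differences in clinical data between the two groups were analyzed".
- **Analysis of Demographic Characteristics and Clinical Data.** "Based on whether the patients had sarcopenic obesity, they were divided into two groups". Tests are the t-test or chi-square.
- **Analysis of Factors Associated with COPD Complicated by Sarcopenic Obesity.** Logistic regression with SO as the outcome.
- **Analysis of the Prognostic Predictive Value.** Length of stay, readmission and mortality are compared between SO patients and patients with no sarcopenia at baseline, by Kaplan-Meier and log-rank.

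**The concern.** A full two-by-two classification is what one needs to tell a combination from its parts. The plan sizes that classification and then does not use it. The analysis text has no four-group test, no main effects of sarcopenia and obesity, no interaction, and no contrast of SO with sarcopenia only or obesity only. The repeated-measures ANOVA in the sample-size sentence is not mentioned again.

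Every SO patient has both traits, while the reference group has each trait only in part. A difference produced entirely by sarcopenia, or entirely by obesity, therefore appears in the SO contrast. At stake is any conclusion that SO, as a combined condition, has its own impact on lung function, phase angle, inflammation or outcome.

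**Working it through.** **1. The plan's own figure.** 33 + 33 + 72 + 72 = 210, not the stated 200. With 67 in each non-sarcopenic group the sum is 33 + 33 + 67 + 67 = 200. I use the stated group sizes and give the alternative where it matters. The effect size, SD, within-patient correlation and number of repeated measures are not given, so the total cannot be re-derived from the ANOVA.

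**2. Clinical-data comparison (SO v all others).** The comparator is 33 + 72 + 72 = 177.

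- Share with sarcopenia: 33/177 = 0.186.
- Share with obesity: 72/177 = 0.407.

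Let sarcopenia shift a variable by Ds and obesity by Do, with no interaction. Then

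E(SO − others) = (1 − 33/177)Ds + (1 − 72/177)Do = 0.81 Ds + 0.59 Do.

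With 67 per non-sarcopenic group the comparator is 167, and the shares are 1 − 33/167 = 0.80 and 1 − 67/167 = 0.60.

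**3. Logistic regression.** The non-SO class is the same 177 patients, of whom 144 (81%) have no sarcopenia. A factor related only to sarcopenia can therefore emerge as a factor for SO. Adjusting for covariates does not change what the outcome variable contrasts.

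**4. Prognostic comparison.** The comparator is 72 + 72 = 144 patients without sarcopenia, half of them obese. The 33 non-obese sarcopenic patients are left out. On a linear scale the contrast carries 1.00 Ds + (1 − 72/144)Do = 1.00 Ds + 0.50 Do. This shows the composition of the contrast; it is not a log-rank calculation.

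**5. How often this would matter.** The plan states no effect sizes, so these effects are assumed. The figures come from 20,000 simulated two-sided t-tests at 0.05, SO v all others, with only one trait having any effect:

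| Assumed effect | Sarcopenia only | Obesity only |
|---|---|---|
| 0.3 SD | 24% significant | 15% |
| 0.5 SD | 55% | 32% |
| 0.8 SD | 91% | 65% |

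**6. Precision of the contrasts.** Inputs are the stated group sizes, a single cross-section and a normal approximation. The detectable difference at 90% power, two-sided 0.05, is (1.96 + 1.2816) × SE.

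| Contrast | SE (SD units) | Detectable |
|---|---|---|
| SO v all others (33 v 177) | √(1/33 + 1/177) = 0.19 | 0.61 SD |
| SO v obese non-sarcopenic (33 v 72) | √(1/33 + 1/72) = 0.21 | 0.68 SD |
| SO v non-obese sarcopenic (33 v 33) | √(1/33 + 1/33) = 0.25 | 0.80 SD |
| Interaction | √(2/33 + 2/72) = 0.30 | 0.96 SD |

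**The case against.** SO yes/no is a legitimate contrast for describing or flagging patients, and the objectives include diagnosis and early screening. No objective asks in so many words whether SO exceeds sarcopenia alone or obesity alone. The clinical-data section speaks of differences, not effects. The ANOVA in the sample-size sentence may mean that a four-group longitudinal analysis was intended and left out of the analysis text. The component contrasts are also less precise.

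Much of this stands, and it rules out several stronger readings:

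- *A component effect will be reported as an effect of SO.* A reader might infer this, but it predicts future wording. It also needs such an effect to exist, and the documents give no effect sizes.
- *The study cannot answer its question.* This goes too far. The limitation applies to the aims on impact and on the effects of inflammation and metabolic disorders, not to the descriptive and screening aims.
- *SO is compared with everyone else throughout.* This is not so for the prognostic analysis, and the 0.81/0.59 shares do not apply there.
- *Sarcopenia or obesity is known to move particular markers.* The documents do not say so, and the argument does not need it.

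The objection does not supply a planned contrast that isolates SO. If a four-group ANOVA was intended, the analysis text has to say so.

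**Conclusion.** The point holds as a mismatch between the groups that are sized and the contrasts that are planned. The clinical-data comparison and the logistic regression mix three kinds of non-SO patient. The prognostic comparison leaves out the group needed to separate SO from sarcopenia alone. None of the three can support a statement that SO has an impact beyond its components.

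The shares rest on the stated group sizes being achieved and on additive effects without interaction. Resolving the 200/210 conflict by taking 67 per non-sarcopenic group moves the clinical-data shares by about one percentage point. The rejection rates depend on assumed effects and are illustrations only.

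**What to change.** - Report each outcome by the four planned groups.
- Model sarcopenia, obesity and their interaction: a repeated-measures model for the continuous primary endpoints, and a Cox model for time-to-event outcomes.
- Prespecify SO v non-obese sarcopenic and SO v obese non-sarcopenic as the contrasts that support any SO-specific statement.
- Use the same group definitions in the prognostic analysis, so that the non-obese sarcopenic patients are included.
- Keep SO v all others as a descriptive comparison.
- Reconcile the total of 200 with the group sizes. Also correct the allocation wording, "a 2:1 ratio for sarcopenic obesity vs. non-sarcopenic groups", which runs opposite to the listed sizes (33 to 72).

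The cost is some rewriting and analysis, with no new patients or measurements. The price is precision: the two SO-specific contrasts detect only differences of about 0.80 and 0.68 SD at 90% power in a single cross-section, and the interaction about 0.96 SD. The interaction should therefore be reported as an estimate with its interval, SO-specific claims should stay cautious, and the plan should say how it handles two contrasts across several outcomes.

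### The prognostic analysis uses body composition only through a cut-off label, and no outcome model takes SMI, body fat or phase angle as graded predictors

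*Combined protocol and SAP*

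**What the plan says.** All references are to the combined protocol and SAP.

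- Data Collection records "skeletal muscle index (SMI), body fat content", a visceral fat index and segmental phase angles, all on graded scales.
- Diagnostic Criteria apply cut-offs to SMI, grip strength, gait speed, BMI, waist and body fat, and then combine the two conditions: "sarcopenic Obesity: Coexistence of sarcopenia and obesity".
- Sample Size Calculation names a repeated-measures ANOVA and four groups: "the study requires 200 participants (33 sarcopenic obese, 33 non-obese sarcopenic, 72 obese non-sarcopenic, and 72 non-obese non-sarcopenic".
- Analysis of Demographic Characteristics and Clinical Data says: "Based on whether the patients had sarcopenic obesity, they were divided into two groups". This introduces a t-test and chi-square comparison of clinical data.
- The section on factors associated with sarcopenic obesity contains the plan's only regression. It is logistic, with the label as the dependent variable.
- The section on prognostic predictive value covers length of stay, readmission for exacerbation and "mortality between COPD patients with sarcopenic obesity and those without sarcopenia at baseline were compared", by Kaplan-Meier with a log-rank test.
- Follow-up Endpoints make 2-year change in pulmonary function, dyspnea score and body composition primary. The analysis text names no method for these changes.

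**The concern.** The title promises a prognostic model, and the objectives include the role of phase angle in predicting adverse outcomes. A log-rank test compares groups. It takes no graded predictor and gives no model. The one regression explains who carries the label, not who exacerbates, is hospitalized or dies. As written, no stated analysis can show whether lower muscle, higher fat or a lower phase angle goes with a worse outcome across their range.

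Three things are at stake:

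- precision, because the labelled group is planned at only 33 patients;
- dependence of the prognostic result on where the cut-offs sit;
- the non-obese sarcopenic patients, who are followed for two years but contribute nothing to the prognostic comparison.

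**Working it through.** **Planned counts.** The plan gives no figure for information loss, so there is none to reproduce. Its group sizes sum to 33 + 33 + 72 + 72 = 210, not the stated 200. I use 210.

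- Label: 33/210 = 15.7%. Sarcopenia: 66/210 = 31.4%. Obesity: 105/210 = 50%.
- Obesity is 33/66 = 50% among sarcopenic and 72/144 = 50% among non-sarcopenic patients, so the planned counts treat the two conditions as independent.
- Prognostic contrast: 33 against 72 + 72 = 144. Patients in neither group: 33, or 15.7% of 210.

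**One normal variable, one cut, linear effect.** The information kept is φ(z)² / [p(1 − p)], where z is the normal cut point for proportion p.

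| p | φ(z) | kept | lost |
|---|---|---|---|
| 0.500 | 0.399 | 0.159/0.250 = 0.64 | 36% |
| 0.314 | 0.355 | 0.126/0.2155 = 0.58 | 42% |
| 0.157 | 0.240 | 0.0577/0.1325 = 0.44 | 56% |

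**The two-component label in the planned contrast.** Let x be muscle deficit and y be fat, both standard normal and independent, cut at 31.4% and 50%.

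- Mean x is 0.355/0.314 = 1.129 if sarcopenic and −0.355/0.686 = −0.518 if not, a difference of 1.647.
- Mean y is 0.399/0.5 = 0.798 if obese and 0 in the whole non-sarcopenic group, a difference of 0.798.
- For a linear score s with group difference d, the information kept relative to a continuous model in all 210 is d² × (33 × 144)/(177 × 210) / var(s) = d² × 0.1278 / var(s).

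| Weights (muscle : fat) | d | var(s) | kept | lost |
|---|---|---|---|---|
| 1 : 1 | 2.445 | 2 | 0.38 | 62% |
| 2 : 1 | 4.092 | 5 | 0.43 | 57% |
| muscle only | 1.647 | 1 | 0.35 | 65% |
| fat only | 0.798 | 1 | 0.08 | 92% |

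A simulation of 2 million draws gave the same losses. With equal weights and a component correlation from −0.3 to 0.5, the loss was 70% down to 50%, although those correlations no longer match the planned counts. Keeping all four groups, again with equal weights, lost 48% down to 30%.

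Label against everyone else lost 65% with equal weights, against 62% for the planned contrast. Under a linear effect, then, leaving out the non-obese sarcopenic group does not itself worsen the loss; those patients simply go unused.

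**The opposite case.** If risk changes only at the label, the label loses 0%. Over the same correlations, a linear continuous model then captures only 28–48% of the variation, or 39–61% with a product term.

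**The case against.** The study concerns a diagnosed condition with stated criteria. Comparing outcomes by diagnosis is a legitimate question, and under a threshold effect it is also the efficient analysis. That stands, and it is why the label should remain the headline contrast.

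Several stronger readings are tempting, but the documents do not support them:

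- **A fixed share of the information, such as 40–60%, is thrown away.** The documents give no such figure and no basis for one. It needs normality, linearity and a single cut variable; other assumptions give anything from 0% to over 90%.
- **The grouping sentence dichotomizes the outcome analysis.** It introduces the comparison of clinical data. The prognostic contrast is defined separately and is not a yes/no split of everyone.
- **The primary endpoints are dichotomized too.** Their analysis is unspecified. The nearest indication is the four-group ANOVA in the sample-size paragraph.
- **Events are few.** No event rate or count is given.
- **Two men just either side of the SMI cut-off are treated as opposites.** That holds only if SMI decides the label. Grip strength, gait speed and the obesity criteria also count, and the plan does not say how the sarcopenia criteria combine.

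Regressing change in body composition on its own baseline also invites mathematical coupling and regression to the mean. The fix has to avoid this.

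**Conclusion.** The concern holds in a limited form. The stated prognostic analysis uses body composition only through a cut-off label, omits 33 of 210 planned patients, and includes no outcome model with SMI, body fat or phase angle as graded predictors. These facts can be read directly from the plan.

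The size of the loss is conditional. For linear effects of normal measures it is 36–56% for a single cut at the planned proportions. For the two-component label in the planned contrast it is about 57–92%, assuming independent components that act in the same direction. For a threshold at the label it is nil. The figures are approximate also because grip strength, gait speed, BMI and waist enter the label, and because the efficiency formula carries over to survival comparisons only for modest effects.

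The group comparison remains valid. This is a low-cost improvement that the promised prognostic model needs.

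**What to change.** Keep the label for description and for the headline Kaplan-Meier contrast. Prespecify one co-reported regression per endpoint in all enrolled patients:

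- **Events:** Cox regression for time to exacerbation, hospitalization and death.
- **Pulmonary function and dyspnea score:** a linear model for 2-year change, adjusted for the baseline value.
- **Predictors:** sex-standardized SMI, sex-standardized body fat and their product as continuous terms, plus whole-body phase angle. Standardizing by sex follows from the sex-specific SMI and body-fat cut-offs.
- **Non-linearity:** check it only where the event count supports the extra terms.
- **Body composition:** model the 2-year value adjusted for baseline, and do not interpret baseline SMI or body fat as predictors of their own change.

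The body-composition measurements are already planned. The cost is four terms per model instead of the single term of a group contrast, before any covariates, and an assumed smooth shape. If risk really does step at the cut-offs, the retained label contrast will show it.
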